### 3. INTRODUCTION

This SAP has been developed after review of the Clinical Study Protocol (final version dated 19 July 2021), and protocol amendment (a) (final version dated 07 September 2021).

This SAP describes the planned analysis of the safety, tolerability and pharmacokinetic (PK) data from this study. A detailed description of the planned TFLs to be presented in the clinical study report (CSR) is provided in the accompanying TFL shell document.

The intent of this document is to provide guidance for the statistical and PK analyses of data. In general, the analyses are based on information from the protocol, unless they have been modified by agreement with Eli Lilly and Company. A limited amount of information concerning this study (e.g., objectives, study design) is given to help the reader's interpretation. For open-label studies, this SAP must be signed off prior to first participant visit for this study. When the SAP and TFL shells are agreed upon and finalized, they will serve as the template for this study's CSR.

This SAP supersedes the statistical considerations identified in the protocol; where considerations are substantially different, they will be so identified. If additional analyses are required to supplement the planned analyses described in this SAP, they may be performed and will be identified in the CSR. Any substantial deviations from this SAP will be agreed upon with Eli Lilly and Company and identified in the CSR. Any minor deviations from the TFLs may not be documented in the CSR.

This SAP is written with consideration of the recommendations outlined in the International Conference on Harmonisation (ICH) E9 Guideline entitled Guidance for Industry: Statistical Principles for Clinical Trials and the ICH E3 Guideline entitled Guidance for Industry: Structure and Content of Clinical Study Reports.

### 4. STUDY OBJECTIVES AND ENDPOINTS

[figure not shown]
Objectives	Endpoints
Primary	

To evaluate the relative bioavailability of RTU (ready to use) and PFOS (powder for oral suspension) suspensions compared to the capsule formulation

Maximum observed drug concentration (<math>C_{max}</math>), area under the concentration versus time curve from time zero to infinity (<math>AUC[0-\infty]</math>), area under the concentration versus time curve from time zero to time <math>t</math> (<math>AUC0-t_{last}</math>), and time to maximum observed drug concentration (<math>t_{max}</math>) of selpercatinib

Secondary	

To evaluate the safety and tolerability of a single 20-mg oral dose of selpercatinib RTU and PFOS suspensions

Summary of the number, severity, and type of treatment-emergent adverse events (TEAEs) and serious adverse events (SAEs)

• To assess the palatability of selpercatinib RTU and PFOS suspensions	• Responses to palatability questionnaire (RTU suspension only)
--	---

## 5. STUDY DESIGN

Study J2G-MC-JZJU (JZJU) will be an open-label, Phase 1 randomized, 3-formulation, 3-period, crossover study in adult healthy male and female participants. The RTU 20-mg suspension and the PFOS 20 mg/mL formulation will be compared to the 20 mg capsule formulation.

[Figure 1](#) below illustrates the study design.

[figure not shown]
### 5.1 Screening

All participants will be screened within 28 days prior to enrolment.

### 5.2 Treatment and Assessment Period

Participants will be admitted to the clinical research unit (CRU) on Day -1. On the morning of Day 1, participants will be randomized to 1 of 3 treatment sequences and will receive single doses of 20 mg selpercatinib on each of Days 1, 8, and 15 as either the RTU suspension, the PFOS, or the capsule, and will be dosed according to the randomization sequence following an overnight fast of at least 10 hours.

The treatment sequences to be used are shown in [Figure 2](#):

**Figure 2: Treatment Sequences for Study J2G-MC-JZJU**

There will be a washout of 7 days between doses of selpercatinib. Participants will remain resident at the CRU for the full duration of the treatment period (i.e., up to Day 21).

## 6. TREATMENTS

The following is a list of the study treatment abbreviations that will be used in the TFLs.

Study Treatment Name	Abbreviation	Treatment order in TFL
20 mg selpercatinib capsule	Capsule	1
RTU selpercatinib 20 mg Suspension	RTU	2
20 mg/mL selpercatinib PFOS	PFOS	3

PFOS = powder for oral suspension, RTU = ready to use

## 7. SAMPLE SIZE JUSTIFICATION

Up to approximately 42 participants will be enrolled to ensure that at least approximately 36 participants complete the study. The sample size for this study is justified based on a precision for the ratio of geometric means and it is represented by the half-width of the 90% confidence interval (CI) of the point estimate on the logarithmic scale. Based on an intra-participant variability of 70% (LOXO-RET-19075), with a probability of 90%, a 90% CI for the ratio of the geometric means for  $C_{max}$  and area under the concentration versus time curve (AUC) will be obtained with a precision about 0.288 in the log scale, which corresponds to approximately 0.334 in the natural scale.

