9.3.2.2. Pharmacokinetic Statistical Inference

Pharmacokinetic parameters will be evaluated to estimate relative bioavailability. For the primary analysis, log-transformed C_{max} , $AUC(0-\infty)$, and $AUC0-t_{last}$ will be evaluated in a linear mixed-effect model with fixed effects for formulation, period, and sequence, and a random effect for subject. The treatment differences will be back-transformed to present the ratios of geometric means and the corresponding confidence intervals (CIs).

For secondary analysis, the t_{max} will be analyzed using a Wilcoxon signed rank test. Estimates of the median difference based on the observed medians, 90% CIs, and p-values from the Wilcoxon test will be calculated. Pharmacokinetic parameters will be summarized using descriptive statistics.

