9.5. Sample Size Determination

Up to approximately 42 participants will be enrolled to ensure that at least approximately 36 participants complete the study. The sample size for this study is justified based on a precision for the ratio of geometric means and it is represented by the half-width of the 90% CI of the point estimate on the logarithmic scale. Based on an intra-subject variability of 70% (LOXO-RET-19075), with a probability of 90%, a 90% CI for the ratio of the geometric means for C_{max} and AUC will be obtained with a precision about 0.288 in the log scale, which corresponds to approximately 0.334 in the natural scale.

10. Supporting Documentation and Operational Considerations

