## 8. DEFINITION OF ANALYSIS POPULATIONS

The “Safety” population will consist of all enrolled participants who received at least one dose of selpercatinib, whether or not they completed all protocol requirement.

The “Pharmacokinetic” population will consist of all participants who received at least one dose of selpercatinib and have evaluable PK data. Participants may be excluded from the PK summary statistics and statistical analysis if a participant has an AE of vomiting that occurs at or before 2 times median  $t_{max}$ .

All protocol deviations that occur during the study will be considered for their severity/impact and will be taken into consideration when participants are assigned to analysis populations.

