#### **9.3.2 Pharmacokinetic Statistical Methodology**

PK parameters will be evaluated to estimate relative bioavailability of the RTU and PFOS suspensions compared to the capsule formulation.

Log-transformed  $C_{\max}$ ,  $AUC(0-\infty)$ , and  $AUC(0-t_{\text{last}})$  parameters will be evaluated in a linear mixed effect model with fixed effects for treatment formulation, period, sequence, and a random effect for participant. The treatment differences between RTU (test) and PFOS (test), and the capsule (reference) formulations will be back-transformed to present the ratios of geometric least squares means and the corresponding 90% CIs.

CCI [REDACTED]

[REDACTED]

[REDACTED]

[REDACTED]

[REDACTED]

The  $t_{\max}$  will be analyzed using a Wilcoxon signed rank test. Estimates of the median difference based on the individual paired differences, 90% CIs, and p-values from the Wilcoxon test will be calculated.

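### Does the 0.288 log-scale precision behind 36 completers misstate what the planned three-formulation model delivers?

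*SAP*

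**What the plan says.** SAP section 7 plans enrolment of up to about 42 participants "to ensure that at least approximately 36 participants complete the study". It measures precision as the half-width of the 90% confidence interval on the log scale, assumes 70% intra-participant variability taken from an earlier selpercatinib study, and asks for that precision with 90% probability. The result is stated as a half-width that "will be obtained with a precision about 0.288 in the log scale, which corresponds to approximately 0.334 in the natural scale". Protocol section 9.5 gives the same figures: "with a precision about 0.288 in the log scale, which corresponds to approximately 0.334 in the natural scale".

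Neither section gives the formula or the degrees of freedom, says whether 70% is a coefficient of variation or a log-scale standard deviation, or names the ratio at which 0.334 applies.

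The primary analysis in SAP section 9.3.2 is a "linear mixed effect model with fixed effects for treatment formulation, period, sequence, and a random effect for participant". Protocol section 9.3.2.2 has the same model: "linear mixed-effect model with fixed effects for formulation, period, and sequence, and a random effect for subject". Each suspension is compared with the capsule, and the SAP reports 90% intervals for the back-transformed ratios.

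**The concern.** Two things stand out when the sentence is checked.

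First, the figure appears to belong to a different analysis from the one planned. It matches a paired comparison of two formulations, whereas the model pools the residual variance over three formulations and has nearly twice the degrees of freedom. The attached 90% probability would then not describe the prespecified analysis. This sentence is the only quantitative support for 36 completers, so a figure in error on the optimistic side would leave the study too small for its stated aim.

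Second, an interval symmetric on the log scale is asymmetric on the ratio scale. A single natural-scale figure of 0.334 could be read as 1 ± 0.334, that is 0.67 to 1.33, which is not the interval implied.

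**Working it through.** **Inputs**

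- n = 36 completers (SAP section 7).
- Two-sided 90% interval and 90% probability of attaining the half-width (SAP section 7).
- Variability 70%, read as a coefficient of variation (assumption): σ = √ln(1 + 0.70²) = √ln(1.49) = 0.6315.
- Three formulations, three periods, three sequences (SAP section 5). A balanced 3×3 Latin square is assumed, because the sequence figure is not visible.

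**Formula**

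Half-width attained with 90% probability = t(0.95, df) × σ × √v × √(χ²(0.90, df)/df), where v is the variance factor of the formulation contrast and equals 2/n for complete profiles. For n = 36, σ√(2/36) = 0.6315 × 0.2357 = 0.14884.

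**Reproducing the stated figure (paired, df = 36 − 1 = 35)**

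- t = 1.6896; χ²(0.90, 35) = 46.059; √(46.059/35) = 1.1472.
- Half-width = 1.6896 × 0.14884 × 1.1472 = 0.2885 (0.28849 unrounded, so 0.288 to three decimals).
- exp(0.28849) − 1 = 0.334.

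Both stated figures are recovered. Other readings fit less well. A two-formulation crossover with 34 df gives 0.2892 (0.335 on the natural scale). Taking 70% as a log-scale standard deviation gives 0.320 with 35 df and 0.305 with 68 df.

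**The visible planned model**

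- Residual df = 108 observations − 36 participants − 2 (period) − 2 (formulation) = 68. An explicit design matrix confirms 68 df and v = 2/36.
- t = 1.6676; χ²(0.90, 68) = 83.308; √(83.308/68) = 1.1068.
- Half-width = 1.6676 × 0.14884 × 1.1068 = 0.2747.
- Ratio of stated to planned: 0.288/0.2747 = 1.048.
- Probability that the half-width is at most 0.288: 0.970.

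**How much slack this leaves**

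| Situation | df | Half-width at 90% probability | P(≤ 0.288) |
|---|---|---|---|
| 36 complete | 68 | 0.275 | 0.970 |
| 34 complete | 64 | 0.284 | 0.928 |
| 33 complete | 62 | 0.2886 | 0.896 |
| 36 in the analysis, 3 missing the last period | 65 | 0.281 | 0.941 |
| 36 in the analysis, 6 missing the last period | 62 | 0.2886 | 0.896 |
| 42 in the analysis, 6 missing the last period | 74 | 0.263 | 0.994 |

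The last row is closest to the plan's own scenario of 42 enrolled and 36 completing, because the PK population keeps anyone dosed with evaluable data. With 36 complete profiles, the true coefficient of variation would have to reach about 74% before the planned model's half-width rose to 0.288.

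**Natural scale**

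exp(0.288) − 1 = 0.334 upward and 1 − exp(−0.288) = 0.250 downward, so the interval around a ratio of 1 is 0.75 to 1.33. Around 0.80 it is 0.60 to 1.07, and around 1.25 it is 0.94 to 1.67. The 0.334 is the larger of the two distances at a ratio of 1.

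**The case for a change.** The best argument for an edit is that a sample size resting on one sentence should be reproducible from that sentence, and this one is not. A reader has to guess the degrees of freedom and the meaning of 70%, and the guess that fits is not the model the same documents specify. Some loss of profiles is also foreseeable. SAP section 8 allows exclusions for vomiting ("Participants may be excluded from the PK summary statistics and statistical analysis if a participant has an AE of vomiting"), and the current text does not show how much loss the design tolerates. If 36 were the total analysed, six missing last periods would use up the margin.

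Part of this stands. The basis is unstated, the 35-df origin is only inferred from the match, and an interval of 0.75 to 1.33 would be clearer than a single 0.334.

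The rest carries less weight. The 36-with-6-missing case leaves out the over-enrolment that the plan provides for exactly this purpose; with 42 in the analysis the half-width is 0.263. Nor is 0.275 the uniquely right replacement. It needs a common within-participant variance across formulations, complete profiles and an assumed set of sequences, and part of SAP section 9.3.2 after the model is blacked out. If variances differ by formulation, or if each suspension is compared with the capsule in a separate pairwise analysis, 35 df is the relevant basis and 0.288 stands as written. A simple calculation that does not depend on pooling is a reasonable planning choice. As for 0.334, both documents define precision on the log scale, where it is symmetric, and neither calls the natural-scale figure symmetric.

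**Conclusion.** The concern does not call for a change. The stated figures contain no arithmetic error: 0.288 and 0.334 are recovered from a standard calculation, and both are given as approximate. Against the visible three-formulation model, 0.288 is conservative by about 0.013 on the log scale (0.288 − 0.2747), roughly 5%, and is met with about 97% probability instead of the promised 90%. The departure is in the safe direction. The visible text sets no acceptance limit or precision target that lies between 0.275 and 0.288. Enrolment, the analysis model, the estimates, the intervals and their interpretation would be the same either way. What is missing is a note of the calculation's basis, which a statistician can reconstruct as shown above.

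This rests on reading 70% as a coefficient of variation, which the match supports. The 0.275 and 97% figures also assume 36 complete profiles, a common within-participant variance and a balanced Latin square. If those assumptions fail so that only the pairwise basis applies, the stated 0.288 is itself the appropriate figure, and the conclusion is the same.

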## 8. DEFINITION OF ANALYSIS POPULATIONS

The “Safety” population will consist of all enrolled participants who received at least one dose of selpercatinib, whether or not they completed all protocol requirement.

The “Pharmacokinetic” population will consist of all participants who received at least one dose of selpercatinib and have evaluable PK data. Participants may be excluded from the PK summary statistics and statistical analysis if a participant has an AE of vomiting that occurs at or before 2 times median  $t_{max}$ .

All protocol deviations that occur during the study will be considered for their severity/impact and will be taken into consideration when participants are assigned to analysis populations.

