2.2. Background

Selpercatinib (LY3527723) is a highly potent and specific small-molecule inhibitor of the RET kinase, with minimal inhibition of other kinase and nonkinase targets.

Selpercatinib doses have been evaluated in healthy participants and patients with advanced or metastatic RET-mutant MTC, advanced or metastatic RET fusion-positive thyroid cancer, other RET fusion-positive solid tumors, and metastatic RET fusion-positive NSCLC across Phase 1, 2, and 3 clinical studies. Across these studies, single oral doses of selpercatinib were administered over a range of 20 to 720 mg. Multiple oral doses of 160 mg/day selpercatinib were administered orally twice daily for 10 days in healthy volunteers. Pediatric dose was selected to be 92 mg/m^2 , (maximum 160 mg BID).

The pharmacokinetics of selpercatinib is characterized by good oral bioavailability, with a t_{max} of approximately 2 hours (range 0 to 8.1 hours). CYP3A4 mediated metabolism constitutes the major route of elimination, and the $t_{\frac{1}{2}}$ is approximately 32 hours in healthy volunteers. The $V_{\text{ss/F}}$ and CL/F of selpercatinib increased with increasing body weight (27 kg to 177 kg). No clinically significant differences in the PK of selpercatinib were observed based on age (15 years to 90 years), or sex. As the PK of selpercatinib have been demonstrated to be linear in the dose range of 20 to 160 mg in adult cancer patients, results from study JZJU can be expected to be applicable across the therapeutic dose range.

More detailed information about the pharmacokinetics (PK) and absorption, distribution, metabolism, and excretion properties of selpercatinib may be found in the IB.

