### **Treatment of Outliers during Pharmacokinetic Analysis**

Application of this procedure to all PK analyses is not a requirement. Rather, this procedure provides justification for exclusion of data when scientifically appropriate. This procedure describes the methodology for identifying an individual value as an outlier for potential exclusion, but does not require that the value be excluded from analysis. The following methodology will not be used to exclude complete profiles from analysis.

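### Minor: SAP 8 excludes early vomiters by participant; in this three-period crossover the affected period is the better unit

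*SAP*

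**What the plan says.** SAP 8 defines the PK population as participants with at least one dose and evaluable PK data, then adds the vomiting rule: "Participants may be excluded from the PK summary statistics and statistical analysis if a participant has an AE of vomiting" no later than twice the median tmax. The rule speaks of participants and is permissive. It mentions neither periods nor profiles.

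Under SAP 5.2 each participant "will receive single doses of 20 mg selpercatinib on each of Days 1, 8, and 15", one formulation per period. SAP 9.3.2 analyses log Cmax and both AUCs in a linear mixed model with formulation, period and sequence as fixed effects and a "random effect for participant". For tmax, the same section says it "will be analyzed using a Wilcoxon signed rank test", with estimates built from individual paired differences.

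No other visible text gives a period-level rule. Protocol 9.2 has no vomiting rule. The outlier procedure in SAP 9.3.1 states: "The following methodology will not be used to exclude complete profiles from analysis". The protocol-deviation sentence in SAP 8 also assigns participants to populations. SAP 9.1 highlights excluded participants in listings and SAP 9.3.1 documents special handling in the CSR. Both make an exclusion visible but do not define its unit.

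**The concern.** Vomiting after one dose casts doubt on that dose's profile. It says nothing about profiles from doses given a week or more apart. A participant who vomits after PFOS still supplies a sound RTU profile and a sound capsule profile, and so a complete within-participant RTU:capsule difference. If the participant is removed, that difference goes too, for Cmax, both AUCs and tmax, although the mixed model was capable of using it.

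What is at stake is some precision in an unaffected comparison, and a rule whose unit is settled before anyone sees the data.

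**Working it through.** **Inputs from the documents.** SAP 7: 36 completers, intra-participant variability 70%, 90% CI, 90% probability, and a CI that "will be obtained with a precision about 0.288 in the log scale". SAP 5.2: three sequences, three doses per participant. SAP 9.3.2: the mixed model.

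**Assumptions.** The sequences are not visible, so a three-sequence Latin square with 12 participants each is assumed. No vomiting rate is given, so k = 1, 2 or 3 of 36 vomiting early, all after PFOS and spread over the sequences, is purely illustrative.

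**Step 1: reproduce the plan's figure.** Reading 70% as a CV, σ_w = √ln(1 + 0.70²) = 0.6315. With n = 36 and df = n − 1 = 35:

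half-width = t(0.95, 35) × σ_w × √(2/36) × √(χ²(0.90, 35)/35) = 1.690 × 0.1488 × 1.147 = 0.2885.

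This matches 0.288, and exp(0.288) − 1 = 0.334 matches the natural-scale figure.

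**Step 2: no event, planned three-period model.** There are 36 × 3 = 108 profiles, and df = 108 − 36 − 4 = 68 (two period and two formulation contrasts). Expected half-width, without the 90%-probability factor: t(0.95, 68) × 0.1488 = 1.668 × 0.1488 = 0.2482.

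**Step 3: participants excluded, k = 3.** n = 33, 99 profiles, df = 99 − 33 − 4 = 62. SE = 0.6315 × √(2/33) = 0.1555. Half-width = 1.670 × 0.1555 = 0.2596 for both ratios. Six sound profiles (2 × 3) are lost with the three affected ones.

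**Step 4: only the affected periods excluded, k = 3.** 105 profiles, 36 participants, df = 105 − 36 − 4 = 65. The standard error comes from fitting the incomplete design.

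| k | Sound profiles lost by excluding participants | RTU:capsule, participants excluded | RTU:capsule, periods excluded |
|---|---|---|---|
| 0 | 0 | 0.2482 | 0.2482 |
| 1 | 2 | 0.2519 | 0.2483 |
| 2 | 4 | 0.2557 | 0.2483 |
| 3 | 6 | 0.2596 | 0.2484 |

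At k = 3 the ratio is 0.2596/0.2484 = 1.045. The affected PFOS:capsule comparison also gains a little: 0.2556 with between-participant log variance 0.30, or 0.2567 by within-participant least squares, against 0.2596. If the affected dose is the capsule, period-level exclusion gives those same values for both ratios.

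**Step 5: tmax.** Excluding a test-formulation period loses one pair; excluding a capsule period loses both. Excluding the participant always loses both. At k = 3 after PFOS, RTU–capsule pairs number 36 under the period rule and 33 under the participant rule, roughly √(36/33) = 1.044 in interval width.

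**Step 6: why results with and without the affected periods are useful.** If an affected PFOS profile is kept and has lost half its exposure, the PFOS AUC ratio is multiplied by 0.5^(k/36): 0.981, 0.962, 0.944 for k = 1, 2, 3. If the capsule is affected, both ratios are multiplied by the inverse: 1.019, 1.039, 1.059. The 50% loss is an assumption. Cmax moves less, or not at all, if vomiting follows the peak.

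**The case against.** The strongest reply is that the wording need not be applied as feared. It permits exclusion without requiring it, and it does not say that every period must go. The PK population already admits participants with incomplete data, and the SAP elsewhere excludes at a finer level (single half-lives, single concentrations). A sensible analyst could drop one period and remain consistent with SAP 8. That stands: the participant-level outcome is allowed, not prescribed. It is still what the sentence literally describes, and nothing visible says otherwise.

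The events are also hypothetical. Protocol 2.3 describes good tolerability in healthy volunteers and lists vomiting among toxicities in patients. At k = 1 the loss is about 1.5% (0.2519 against 0.2483). This stands too, and fixes the grade at minor.

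Part of SAP 9.3.2 is redacted, and the detail of the outputs "is provided in the accompanying TFL shell document", which was not available. A with/without analysis may already exist there.

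Four stronger readings are tempting, and the documents do not support them.

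- A reader might infer that the rule misses tmax. It does not: it covers PK summary statistics and statistical analysis without restriction, and tmax is a PK endpoint. A period-level rule only needs to state which pairs are lost.
- A reader might conclude that exclusion must be compulsory. That is debatable. Vomiting may be formulation-related, so automatic deletion could hide a real formulation effect.
- A reader might suspect planned selective exclusion because the study is open label. Nothing in the documents shows this.
- A reader might set the full-model 90%-probability value for 33 participants, 0.2886 at df 62, beside the planned 0.288 and see no loss. The bases differ. On the SAP's own basis, n = 33 and df = 32 give 1.694 × 0.1555 × 1.154 = 0.304.

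**Conclusion.** The point holds as a minor, inexpensive improvement. SAP 8 sets the early-vomiting exclusion at participant level in a design where the period is the natural unit and the planned model can use the remaining periods. Under the assumed 3 of 36 early vomiters after PFOS, the untouched RTU:capsule half-width is 0.2596 rather than 0.2484. This rests on the 70% CV, 36 completers, an assumed Latin square and an invented event count; with fewer events the difference shrinks, and with none it vanishes. The plan estimates relative bioavailability and shows no equivalence limit, so no visible pass/fail conclusion depends on the choice.

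Which median tmax sets the window is a missing detail rather than an error. With tmax of "approximately 2 hours (range 0 to 8.1 hours"), as Protocol 2.2 reports, the limit would be about 2 × 2 = 4 hours.

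**What to change.** In SAP 8, make the affected period the unit. If a participant vomits at or before twice the median tmax after a dose, the PK parameters of that period are the ones subject to exclusion, and the participant's other periods stay in. For the Wilcoxon analysis of tmax, state that only pairs containing the excluded period are lost. Say whether the median tmax is per formulation or pooled.

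Report the mixed-model results with and without the affected periods, unless the redacted part of SAP 9.3.2 or the TFL shells already provide this. Whether exclusion in the main analysis is compulsory or follows stated criteria is for the sponsor to decide, and should be fixed before PK results are seen.

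The cost is a few lines of SAP text and one extra model run. The downside is slightly less data for the affected formulation than if its period were kept, including any period in which vomiting did not reduce absorption. The second set of results shows how much that matters.
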